
Sample Size Justification: The primary goal in Aim 1 is to estimate the proportion of participants who are compliant in the two groups. A sample of 20 subjects per group provides a 95% confidence interval for compliance within group with a width < 0.46 assuming at least 50% compliance. Compliance is anticipated to be greater than 50% which will yield a more precise estimate. The primary goal in Aim 2 is to estimate the change in LUP-QOL between baseline and 12 months post intervention within and between each treatment. Mean change from baseline with group and the difference in change between groups will be estimated using contrast statements from a linear mixed model of LUP-QOL score with fixed effects for treatment, time, and the treatment by time interaction and a random subject effect. A sample of 20 participants measured at 3 time points and assuming an AR(1) correlation with $\rho=0.5$ allows us to estimate a two-sided 95% confidence interval for change in LUP-QOL from baseline within group to within 0.57 standard deviations (1). A sample size of 20 subjects per treatment group also allows us to estimate a 95% confidence interval for the difference in change in LUP-QOL from baseline between the two groups to within 0.64 standard deviations from the mean assuming common standard deviation between the groups.

E. PROTECTION OF HUMAN SUBJECTS

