Overview of Study Design. The Care-coordination Approach to Learning Lupus Self-Management (CALLS) study is a double arm, pre-post pilot designed to examine whether modeling and reinforcement from a lay patient navigator/care coordinator improves disease self-management, indicators of disease activity, health related quality of life (HRQOL), and 30-day readmission in SLE inpatient admissions. We will recruit 40 patients (20 questionnaires and phone sessions and 20 questionnaires only) with active SLE upon hospital admittance at the Medical University of South Carolina (MUSC). The lay patient navigator/care coordinator will be trained to deliver intervention content by twelve weekly telephone sessions carried out across the course of the study. All participants will be assessed using validated measures of patient reported outcomes at baseline, mid-intervention (6 weeks post-enrollment), and immediately following the intervention (12 weeks post-enrollment). Outcomes for patients who agree to phone sessions will be compared with the outcomes of patients who opt to participate in questionnaires only. The study will last 12 months with recruitment and enrollment over 6 months, 3 months for intervention delivery and 3 months for data analysis.

Study Population. The total number of individual patients with systemic lupus erythematosus (SLE) currently being followed by clinicians at MUSC is 1,159 in the past six months that had this encounter diagnosis and 1,526 with this diagnosis in the chart history or problem list or encounter diagnosis, of which approximately 60% are African American and 90% are female. This will allow for the assessment of impact and cost savings/effectiveness according to underrepresented racial and gender categories. The target population for this study will be SLE inpatient admissions. There are approximately 35 SLE and Scleroderma hospital admissions each month, so it is expected that over a 3-month recruitment period, we will be able to recruit 40 participants (20 questionnaires and phone sessions and 20 questionnaires only).

Recruitment of Lay Patient Navigator/Care Coordinator

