Admitted SLE patients will be referred by their physician for participation in the study, who will provide a letter that will explain the study and provide participants a number to call if they have questions or concerns prior to agreeing to participate. Participants who indicate interest in the study will be immediately screened for eligibility, and if eligibility criteria are met, informed consent will be obtained. Once a patient has been consented, they will be randomized to membership in one of the two study arms. assigned to the intervention (complete questionnaires and phone sessions) or control (complete questionnaires only) arm, and the rest of the recruitment visit will include baseline self-report assessments and scheduling of phone sessions (if applicable). Preliminary data from our group suggests that those participants with the worse outcomes at baseline experienced the largest gains post-intervention, so the proposed intervention focuses on patients with high needs (as indicated by hospital admission) to reach those with the greatest potential for benefit from supportive services. This approach could ultimately incorporate the lupus nephritis risk prediction model/tool being developed by [name] to prevent renal failure and admissions due to renal flares.

Inclusion criteria for SLE patients include: 1) Hospital admission for SLE-related issue; 2) clinical diagnosis of systemic lupus erythematosus (SLE) from a physician; 3) 18 years of age or older; 4) able to provide informed consent and take part in ongoing assessment/evaluation activities (self-reported questionnaires); 5) able to commit to duration of study (3 months); 6) able to communicate in English; and 7) have an active phone line (landline or cell phone) for the duration of the study, if agreeing to phone sessions with the lay patient navigator/care coordinator. Exclusion criteria include: 1) cognitive impairment; 2) acute decompensation of chronic conditions precluding participation; 3) conditions that preclude participation in assessments (e.g. blindness or deafness); and 4) terminal illness or life expectancy less than 6 months as evaluated by physician.

Lay Patient Navigator/Care Coordinator Service Elements.

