2. ADEQUACY OF PROTECTION AGAINST RISKS

a. Recruitment and Informed Consent

- Describe plans for the recruitment of subjects (where appropriate) and the process for obtaining informed consent. If the proposed studies will include children, describe the process for meeting requirements for parental permission and child assent.
- Include a description of the circumstances under which consent will be sought and obtained, who will seek it, the nature of the information to be provided to prospective subjects, and the method of documenting consent.

After obtaining approval from the IRB, admitted SLE patients will be referred by their physician for participation in the study, who will provide a letter that will explain the study and provide participants a number to call if they have questions or concerns prior to agreeing to participate. Participants who indicate interest in the study will be immediately screened for eligibility, and if eligibility criteria are met, informed consent will be obtained. Once a patient has been consented, they will be randomized to membership in one of the two study arms. assigned to the intervention (complete questionnaires and phone sessions) or control (complete questionnaires only) arm, and the rest of the recruitment visit will include baseline self-report assessments and scheduling of phone sessions (if applicable).

b. Protection against Risk

- Describe planned procedures for protecting against or minimizing potential risks, including risks to confidentiality, and assess their likely effectiveness.
- Where appropriate, discuss plans for ensuring necessary medical or professional intervention in the event of adverse effects to the subjects.
- Studies that involve clinical trials (biomedical and behavioral intervention studies) must include a description of the plan for data and safety monitoring of the research and adverse event reporting to ensure the safety of subjects in Section 4 below.

Given the complexity of SLE and the overall study goal to provide modeling and reinforcement by a lay patient navigator to lupus patients to encourage them to engage in activities that promote the learning of disease self-

management skills and support their practice of these learned skills, every attempt will be made to ensure that the study/navigation does not negatively impact the patient. To address this potential concern the following approach will be implemented:

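### The protocol forms the two groups by patient choice in one section and by randomization in two others, which leaves the Aim 2 between-group contrast undefined

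*Protocol*

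**What the plan says.** The protocol describes how the arms arise in four places.

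- **Section D, Overview of Study Design.** The study "is a double arm, pre-post pilot designed to examine whether modeling and reinforcement". It has 20 patients with questionnaires and phone sessions and 20 with questionnaires only. The comparison is then given as: "Outcomes for patients who agree to phone sessions will be compared with the outcomes of patients who opt to participate in questionnaires only". Randomization is not mentioned in this overview.
- **Section D, Recruitment of SLE patients.** After screening and consent: "Once a patient has been consented, they will be randomized to membership in one of the two study arms".
- **Section E.2.a, Recruitment and Informed Consent.** The same text is repeated, and in both places it runs into a broken sentence: "they will be randomized to membership in one of the two study arms. assigned to the intervention".
- **Inclusion criterion 7** (Section D, Recruitment of SLE patients, and again in Section E.1.a). The patient must "have an active phone line (landline or cell phone) for the duration of the study, if agreeing to phone sessions".

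The Aim 2 analysis estimates the between-group difference in change from baseline with a linear mixed model. The Sample Size Justification lists the model terms: treatment, time, their interaction and a random subject effect.

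**The concern.** The overview lets the patient's decision about phone sessions define the group. The recruitment text lets a random assignment define it. These are two different designs, and the between-group contrast means something different in each.

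Under choice, patients who accept weekly sessions may differ from those who decline in ways that also affect how they change over 12 weeks. The protocol itself points to one such route: Section D, Recruitment of SLE patients, reports from the group's preliminary data that patients who were worse at baseline gained most. If uptake is related to baseline status, the arms would be expected to change differently even with no effect of the navigator.

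Under randomization, a comparison of those who agree with those who opt out, read literally, goes by uptake and not by assigned arm.

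The result is meant for later use: Aim 2 produces effect sizes for sizing a future R01. A distorted contrast would carry into that calculation.

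**Working it through.** **1. The passages side by side**

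| Place | How the group is determined |
|---|---|
| D, Overview of Study Design | The patient agrees to sessions or opts for questionnaires only |
| D, Recruitment of SLE patients | Randomized after consent |
| E.2.a, Recruitment and Informed Consent | Randomized after consent |
| Criterion 7 (D and E.1.a) | Phone line needed only if the patient agrees to sessions |

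The choice wording is not confined to one sentence. The recruitment section of D contains both versions: randomization in the procedure and choice in criterion 7.

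**2. Does the stated model deal with selection?** With fixed effects for treatment, time and treatment by time, the contrast is (mean change, sessions arm) minus (mean change, questionnaires-only arm). It lets the arms start at different levels but does not condition on baseline or on any other covariate. If a factor predicts change and is unevenly spread between arms, the contrast carries that imbalance. Process Measures and Secondary Outcomes lists covariates to be collected (education, income, insurance, health literacy, self-efficacy, depression and others), but the protocol states no adjustment for them.

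**3. Effect on Aim 1.** The Sample Size Justification makes compliance in the two groups the primary Aim 1 quantity. Suppose a patient declines sessions.
- Under choice, that patient belongs to the questionnaires-only arm and does not lower compliance in the sessions arm.
- Under randomization to sessions, the same patient is noncompliant. With 20 in the arm, each such patient lowers the proportion by 1/20 = 5 percentage points.

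**4. The stated precision.** The protocol gives a 95% half-width of 0.64 SD for the between-group difference in change.
- Inputs: 20 per arm, hence 38 degrees of freedom.
- Formula: half-width = t(0.975, 38) × SD × √(2/20).
- Result: 2.024 × 0.316 = 0.640 SD, with SD that of the change score (equivalently, a baseline to follow-up correlation of 0.5).

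The stated figure reproduces on that basis. The formula contains only n and the SD, so it is the same whether arms are chosen or randomized. It describes precision and cannot reveal bias.

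**5. What a bias would do to the interval (assumed values only).** The documents give no figure for selection bias. For an assumed bias b in SDs of change, with SE = √(2/20) = 0.316, the coverage of a nominal 95% interval is approximately Φ(1.96 − b/SE) − Φ(−1.96 − b/SE):
- b = 0.1: about 94%
- b = 0.2: about 90%
- b = 0.3: about 84%
- b = 0.5: about 65%

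This shows only how an interval of this width reacts to bias. It is not an estimate of the bias in this study.

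**The case against.** The best counter-argument is that the operational steps are clear. Both recruitment sections give the order as screening, consent, then randomization, and the analysis text speaks of treatment groups, not of uptake. The broken sentence after the randomization statement looks like an incomplete edit, in which case the overview sentence and criterion 7 may be leftovers. That is plausible but remains inference. The overview is current text, and a reader cannot tell from the document which version was meant to survive.

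A reader might infer more than the documents support:

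- *That the trial is non-randomized and its contrast confounded.* This does not follow. If the recruitment text governs, the contrast is randomized.
- *That an as-treated analysis is planned.* The overview sentence reads that way if patients are randomized, but the Aim 2 and sample size text does not define groups by uptake, and analysis-set rules may stand in a statistical analysis plan that is not shown. The same holds for covariate adjustment.
- *That patients without a phone could be assigned sessions that cannot be delivered.* Section D, Phone sessions, allows the weekly session by telephone or in person.
- *That criterion 7 makes eligibility depend on the arm.* It is checked before any arm is known. As written it depends on willingness to have phone sessions, which is still the wrong basis when assignment comes later.
- *That the bias can be sized against the earlier peer-mentoring pilot's effect sizes (above 0.3).* Any such figure needs assumed inputs for imbalance and prognostic strength. Those effect sizes also come from an uncontrolled study and are changes following participation, so they are not a like-for-like benchmark for a between-arm bias.

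One might also say that uptake and assignment will coincide, since the protocol expects all scheduled sessions to occur. But the Sample Size Justification assumes only that compliance is at least 50%, so the two cannot be taken as the same.

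**Conclusion.** The contradiction is real and stands in current text. The overview compares groups formed by choice, two recruitment sections randomize, and both copies of criterion 7 follow the choice logic. Followed as written, the overview comparison is by choice or uptake, and the model stated in the protocol would not remove the resulting selection. The Aim 2 between-group estimate and the meaning of compliance in Aim 1 both depend on which version governs.

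The conclusion is conditional: the contrast is open to self-selection if the overview is followed, and is protected if patients are randomized and compared as assigned. The size of any bias cannot be derived from the documents. Sample size and the stated precision figures are unaffected. How the arms are formed has to be settled before enrolment, because it cannot be repaired by analysis afterwards.

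**What to change.** The investigators should first confirm the allocation method, then reconcile the sections.

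**If randomization is intended**, as both recruitment sections state:
- Replace the overview sentence with: 'Outcomes of patients randomized to questionnaires plus phone sessions will be compared with outcomes of patients randomized to questionnaires only, analysed as randomized regardless of sessions completed.'
- Reword criterion 7 in Sections D and E.1.a so that it applies identically to every patient before randomization and does not turn on agreeing to phone sessions. Reconcile it with the allowance for in-person sessions in Section D, Phone sessions.
- Repair the broken sentence after the randomization statement in Sections D and E.2.a.

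**If allocation by choice is intended:**
- Delete the randomization text in Sections D and E.2.a.
- State adjustment for the baseline covariates already collected.
- State that the between-group contrast is non-causal.

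**Cost.** Under randomization the change is wording, with 20 per arm and the precision figures kept. If a phone line is required of everyone, a few patients without one become ineligible, which is a change of eligibility and should be acknowledged as such. Under choice, the cost is a weaker claim from Aim 2.

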Treatment Fidelity. Drs. [name] and [name] will deliver training for the lay patient navigator/care coordinator at the onset of the study. They will be given parameters for their roles and instructed on how to handle potential issues that may arise. After the initial training, the lay patient navigator/care coordinator will continue to meet with the PI weekly to identify challenges and reinforce the guidelines for their role.[185] They will be required to submit logs of the number of calls made, number of hours spent with patients, and content covered during that week. Self-report assessments will be used to track the effectiveness of their services.

Data Collection Schedule. Study questionnaires were carefully chosen based on available evidence of previous validation and their ability to measure key elements of the study aims. The primary method of data collection will be face-to-face interview. All study visits will take place in an MUSC affiliated hospital, the Research Nexus or comparable private location on the campus of MUSC. Indicators of medication adherence will be extracted from the electronic medical records. Financial data will be extracted from the research data warehouse for historical and patient-specific data for cost effectiveness. The MUSC REDCap system will be used for data management.

Primary Outcomes. Primary outcomes of quality of life, self-management, and disease activity (including medication adherence) will be measured using the Lupus Quality of Life Questionnaire (LUP-QOL), which incorporates the Medical Outcomes Study (MOS) Short Form 36 Health Survey (SF-36) and the Functional Assessment of Chronic Illness Therapy-Fatigue (FACIT-F);[187-189] the Patient Activation Measure (PAM), [190,191] which assesses an individual's knowledge, skill, and confidence for managing their health and healthcare; medication refill data in electronic medical records to further validate treatment engagement/adherence; 30-day readmission data to assess cost savings or deficit (compared to historical data from the prior year); and the Systemic Lupus Activity Questionnaire (SLAQ),[192] which is based on items from the physician-rated Systemic Lupus Activity Measure (SLAM) that could be self-reported.[193,194]

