Aim 2 - Estimation of effect sizes for calculating sample size for future R01: Analyses for Aim 2 of the pilot/feasibility study will focus on estimation of preliminary effectiveness as determined by: (a) change in quality of life; (b) change in self-management; and (c) change in disease activity (self-reported). Estimates of effect sizes for outcome variables will be reported as point estimates (mean differences between pre-post measures, as appropriate) and interval estimates (95% CI) to provide a preliminary indication of the presence of a clinically important treatment effect.[201-203] After studying the distributions of baseline characteristics, we will use a linear mixed-effects regression model to estimate the difference in the change from baseline between the two groups. Least squares means for each outcome variable will be compared at the primary time point (week 12) and at intermediate time points (week 6 or 12) using model contrasts to estimate the corresponding 95% CI for the estimates of the difference in outcome means (effect sizes) between and within treatment group.

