- Describe any data that will be recorded on the human subjects involved in the project.
- Describe the linkages to subjects, and indicate who will have access to subject identities.
- Provide information about how the specimens, records, or data are collected and whether material or data will be collected specifically for your proposed research project.

1. Research Material & Data: Sources of research material include medical records and research questionnaires.
2. Linkages to Subjects: Subjects will provide identifying information in addition to research data. Paper documents pertaining to this study will be stored in locked file cabinets in both the clinical center and the data

management center, and data will be entered into secure, password-protected web databases developed for this study. A database of name, contact address, telephone number, and other research identification numbers will be stored separate from the study database, for purposes of audit by the MUSC IRB, if necessary. Access to study data will be limited to research personnel.

3. Collection of Data and Specimens:

Personnel: A part-time lay patient navigator will be responsible for consent, enrollment and data collection, a part time health economist will be responsible for accessing and analyzing resource use and cost data, and a part-time data coordinator (DC) will be responsible for data management and analyses for patient reported outcomes. **Data Collection Schedule:** At the baseline visit, the lay patient navigator will give detailed explanation of the study, the reimbursement schedule, and obtain consent. Participants will complete a questionnaire that captures demographics, health literacy, coping, disease activity, disease self-management, anxiety, depression, and quality of life. The lay patient navigator will review study goals, establish the schedule of study sessions, obtain contact information (primary and alternate telephone numbers), and receive study materials. After the baseline assessment, follow-up assessments will be conducted at 6 weeks and 12 weeks. As much as possible, research visits will be scheduled on the same day as their clinic visit.

c. Potential Risks

- Describe the potential risks to subjects (physical, psychological, social, legal, or other), and assess their likelihood and seriousness to the subjects.

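### Arm assignment precedes the baseline questionnaires in the same visit, so the self-reported Aim 2 change scores can be biased by knowledge of the arm

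*Protocol*

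**What the plan says.** **Order of the recruitment visit.** Section D, Recruitment of SLE patients, puts allocation directly after consent: "Once a patient has been consented, they will be randomized to membership in one of the two study arms". The baseline questionnaires follow: "the rest of the recruitment visit will include baseline self-report assessments and scheduling of phone sessions (if applicable". Section E.2.a, Recruitment and Informed Consent, gives the same sequence: "arm, and the rest of the recruitment visit will include baseline self-report assessments and scheduling of phone sessions (if applicable".

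**Who collects the data, and how.** Section E.1.b states: "A part-time lay patient navigator will be responsible for consent, enrollment and data collection". Section D, Data Collection Schedule, adds: "The primary method of data collection will be face-to-face interview".

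**What the baseline feeds.** The Aim 2 outcomes are listed as "a) change in quality of life; (b) change in self-management; and (c) change in disease activity (self-reported". Under Primary Outcomes the instruments are LUP-QOL, PAM and SLAQ. For the analysis, "we will use a linear mixed-effects regression model to estimate the difference in the change from baseline between the two groups". The Sample Size Justification specifies fixed effects for treatment, time and their interaction, with a random subject effect. It gives a half-width of 0.64 SD for the between-arm difference in change with 20 patients per arm.

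**The concern.** A baseline measurement in a randomised comparison should be one that the allocation cannot have influenced. Here the patient is allocated first and then answers subjective questions about quality of life, activation and disease activity. The calls are arranged in the same visit for one arm only, and the person responsible for data collection is the one who will make those calls. Hope, disappointment or a wish to please can colour the answers differently in the two arms.

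Aim 2 subtracts these answers from the week 12 answers, so an arm-specific reaction at baseline enters the between-arm contrast with the sign reversed. The stated purpose of Aim 2 is to supply effect sizes for planning a larger trial, so an error here would carry into that trial's sample size. It could not be repaired later, because baseline cannot be collected again and a reaction to the assignment cannot be told apart from a true baseline level.

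**Working it through.** **Step 1. Does any section put baseline before assignment?**

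| Place in the protocol | What it fixes |
|---|---|
| D, Recruitment of SLE patients | consent, randomisation, then baseline and call scheduling |
| E.2.a, Recruitment and Informed Consent | the same order |
| D, Phone sessions | baseline before the calls, which is not the same as before assignment |
| E.1.b, Collection of Data and Specimens | explanation and consent, questionnaire, session schedule; randomisation not placed |

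Two sections give assignment first and none gives baseline first. E.1.b is compatible with either order, so it neither confirms nor corrects the other two. No section describes blinding or withholding of the arm until the questionnaires are done.

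**Step 2. The plan's between-arm half-width.** With n = 20 per arm, in SD units, and r the correlation between baseline and week 12:

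half-width = t(0.975; 38 df) × √(2(1 − r)) × √(2/n)

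- r = 0.5: 2.024 × 1.000 × 0.3162 = 0.640, which reproduces the stated 0.64.
- r = 0.25 (the lag-2 value under AR(1) with ρ = 0.5): 2.024 × 1.225 × 0.3162 = 0.784.

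The two results are used only as yardsticks below.

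**Step 3. How a baseline shift reaches the estimate.** With complete data, the treatment-by-time contrast at week 12 is

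D = (Y12 − Y0) intervention − (Y12 − Y0) control.

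Let knowledge of the arm move the between-arm difference in Y0 by d, and let a fraction p of that shift still be present at week 12. The bias in D is −(1 − p)d. It equals d in size when p = 0 and vanishes when p = 1. If baseline is instead used as a covariate, with slope about r, the bias at p = 0 is about r × d in size.

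**Step 4. Illustration.** The protocol gives no value for d, so 0.1 to 0.3 SD is an assumed range. For p = 0:

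| d (SD) | Bias in D (SD) | Share of 0.64 | Share of 0.784 | Bias with baseline as covariate, r = 0.25 to 0.5 (SD) |
|---|---|---|---|---|
| 0.1 | 0.1 | 16% | 13% | 0.025 to 0.05 |
| 0.2 | 0.2 | 31% | 26% | 0.05 to 0.10 |
| 0.3 | 0.3 | 47% | 38% | 0.075 to 0.15 |

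**Step 5. What this does to the interval.** With no true effect, the chance that the 95% interval excludes zero follows from a noncentral t distribution with 38 df and noncentrality d/SE. SE is 0.3162 at r = 0.5 and 0.3873 at r = 0.25. For d = 0.1, 0.2 and 0.3, the chance is about 6%, 9% and 15% at r = 0.5, and about 6%, 8% and 12% at r = 0.25, against a nominal 5%.

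**The case against.** **Knowledge of the arm is not stated.** The allocation sentence is visibly broken in both sections, and E.1.b could be followed with the arm disclosed after the questionnaire. That is right as far as it goes: a reader might infer that the protocol proves patients know their arm at baseline, and it does not. It does write assignment first, twice, and describes no safeguard. Knowledge of the arm is therefore a strong inference, not a documented fact.

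**The arms may not be randomised at all.** The Overview of Study Design describes arms formed by the patient's own choice, and inclusion criterion 7 points the same way. This contradicts the two recruitment passages and has to be settled, because reordering protects a randomised comparison only. Under either description the patient can know the arm at baseline.

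**The effect need not be one-for-one, nor favour the intervention.** This stands. A reaction that lasts to week 12 cancels in part or in full. Hope that lifts the intervention arm's baseline, or disappointment that lowers the control arm's, would understate benefit; the reverse is also possible.

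**Some stronger readings fail.** A reader might conclude that every change from baseline is affected, but refill, readmission and cost data come from records. A reader might call baseline adjustment invalid, but it shrinks the bias without removing it. The effect sizes above 0.3 cited from the earlier peer-mentoring pilot are a poor yardstick, since that pilot was an uncontrolled pre-post study. Loss of patients on learning their arm adds little: allocation and baseline fall in one visit, and such a patient would lack a week 12 value under either order.

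**It is a 40-patient pilot.** Aim 2 has no confirmatory test, and the week 6 and week 12 answers would remain unblinded self-report. This limits the weight of the point but does not justify the order, since correcting it costs essentially nothing.

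**Conclusion.** The concern holds in a limited form. The protocol fixes assignment before the baseline questionnaires and describes nothing to keep the arm from the patient or the interviewer. The between-arm difference in change for LUP-QOL, PAM and SLAQ can therefore be biased, in a direction that cannot be predicted from the document.

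The size cannot be derived either. Under an assumed differential shift of 0.1 to 0.3 SD that has disappeared by week 12, the bias is up to 0.1 to 0.3 SD. That is less than half of the plan's own 0.64 SD half-width, and smaller still with persistence or baseline adjustment. The conclusion rests on two assumptions: that patients learn their arm when it is assigned, and that allocation is by randomisation as the two recruitment passages say. This is an avoidable weakness to correct before enrolment. It does not show that the Aim 2 estimates will be wrong or that benefit will be exaggerated.

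**What to change.** In Section D (Recruitment of SLE patients) and Section E.2.a, and consistently in Section E.1.b, state one sequence: consent; completion of all baseline questionnaires; generation or disclosure of the randomised assignment; scheduling of calls for the intervention arm. Repair the broken allocation sentence at the same time.

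Reconcile the Overview of Study Design and inclusion criterion 7 with randomisation, so that it is clear there is an assignment to withhold.

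The cost is a few sentences. The visit, the questionnaires, the staff and the 40 patients stay as they are. Having someone other than the navigator administer the questionnaires would add protection, but the reordering does not depend on it.
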